14.7 FOLLOW-UP OF PATIENT AFTER AE

The investigator is responsible for ensuring the follow-up of any patient who experiences an AE during the investigation.

All AEs experienced by a patient, irrespective of the suspected causality, will be monitored until the event has resolved, any abnormal laboratory values have returned to baseline or stabilised at a level acceptable to the investigator and Medical Expert, until there is a satisfactory explanation for the changes observed.

In case of SAE, the investigator or an appropriate qualified physician must re-examine the patient at regular intervals until the event has resolved or stabilised at a level acceptable to the investigator and Medical expert and/or until completion of the “Last Patient Last Visit”.

Further follow up information will be reported to Laboratoires THÉA.

14.8 MANAGEMENT OF PREGNANCY

In case of the investigator or an appropriate qualified physician is informed that a patient becomes pregnant while taking IMDs, she will be immediately withdrawn from the investigation and she will be followed until the outcome of the birth is available.

A communication will be sent by the investigator to Laboratoires THÉA as soon as he/she has knowledge of the normal outcome. Conversely, if the outcome of the pregnancy meets the criteria of SAE (e.g spontaneous or therapeutic abortion, stillbirth, neonatal death, congenital abnormality, birth defect), the investigator should follow the procedure for reporting of SAEs.

Handling of a pregnancy occurring throughout the investigation follows the same reporting procedure as per an SAE notification.

Upon medically confirmed pregnancy during the investigation the investigator must:

- Report immediately (maximum 24 hours) the pregnancy status to Laboratoires THÉA using the email [REDACTED]
- Discontinue the IMD.

- Perform / ensure assessment until delivery of a thorough investigation of the fetus
- Remain responsible for any medical advice he/she might sought thus making appropriate decision upon pregnancy
- Report to Laboratoires THÉA Follow-Up data / update(s) using the SAE form

14.9 LIST OF FORESEEABLE AES AND ANTICIPATED ADVERSE DEVICE EFFECTS, TOGETHER WITH THEIR LIKELY INCIDENCE, MITIGATION OR TREATMENT

According to the IMD leaflets, the following side effects are known: rare possibility of mild eye irritation and ocular redness.

When you use eye drops, you might experience disturbing symptoms such as burning sensation, stinging sensation, foreign body sensation in the eye and blurred vision for a short time.

15. VULNERABLE POPULATION

This clinical investigation will not be conducted in children, or in any other vulnerable populations. If the patient is not capable of giving consent, the written consent of the patient's legal representative will be required before participation in the investigation (see **Section 13**).

16. SUSPENSION OR PREMATURE TERMINATION OF THE CLINICAL INVESTIGATION

16.1 TEMPORARY HALT OF THE INVESTIGATION

The Sponsor may suspend the clinical investigation for any safety, ethical or administrative reason at any time. The investigator, IEC or CA may suspend or prematurely terminate participation at the investigational sites for which they are responsible.

As required by the Clinical Trials legislation, in the case of temporary halt of the clinical investigation:

- For reasons not affecting the benefit-risk balance, the Sponsor shall notify each country concerned through the EU portal within 15 days from the temporary halt of the clinical investigation
- For reasons of a change of the benefit-risk balance the Sponsor shall notify without undue delay but not later than in 15 days of the date of the temporary halt in each country concerned through the EU portal of the reasons for such action and, follow-up measures for the patient.
- For an exceptional circumstance (*e.g.* COVID-19 pandemic), the Sponsor will follow the CAs' recommendations.

When a temporarily halted clinical investigation is resumed the Sponsor will inform all involved investigators. The Sponsor must notify IEC/IRB/CA with the reason(s) for the suspension, as per the applicable regulatory requirement(s).

If a temporarily halted clinical investigation is not resumed within two years, the expiry date of this period or the date of the decision of the sponsor not to resume the clinical investigation, whichever is earlier, shall be deemed to be the date of the end of the clinical investigation.

The restart of the clinical investigation following a temporary halt shall be deemed to be a substantial modification.

16.2 EARLY TERMINATION OF THE INVESTIGATION

The Sponsor or the investigator has the right to terminate the clinical investigation for any safety, ethical or administrative reason at any time. As far as possible, this should occur after mutual consultation.

As required by the Clinical Trials legislation, in the case of early termination of the clinical investigation:

- For reasons not affecting the benefit-risk balance, the Sponsor shall notify each country concerned through the EU portal of the reasons for such action and, when appropriate, follow-up measures for the patient
- For reasons of a change of the benefit-risk balance the Sponsor shall notify without undue delay but not later than in 15 days of the date of early termination in each country concerned through the EU portal of the reasons for such action and, follow-up measures for the patient.

The investigator, IEC or CA may prematurely terminate participation at the investigational sites for which they are responsible.

Should the investigation be terminated prematurely, all investigational materials (IMDs, completed, partially completed, etc.) must be returned to the Sponsor or the Sponsor's representative as if the investigation had been completed.

Laboratoires THÉA shall have the right to terminate the investigation at any time on written notice to the investigator. Without in any way limiting this right, Laboratoires THÉA would normally only terminate the investigation in the following circumstances:

- Occurrence of
 - new events related to the conduct of a investigation or the development of an IMD likely to affect the safety of patient, such as:
 - a SAE which could be associated with the investigation procedures, and which could modify the conduct of the investigation
 - a significant hazard to the patient population such as lack of performance of an IMD used for the treatment of a life-threatening disease
 - a major safety finding from a newly completed animal study/investigation (such as carcinogenicity)
 - a temporary halt of an investigation for safety reasons if the investigation is conducted with the same IMDs in another country by the same Sponsor
- If severe and/or serious AEs with the IMD in human or animal studies should indicate discontinuation of the investigation.
- If Laboratoires THÉA should wish to discontinue the investigation for commercial reasons.
- If Laboratoires THÉA had reasons to believe that the investigation could not be satisfactorily completed, including, but not limited to, the reason that inadequate numbers of patient could be enrolled or insufficient centres found within the necessary time.

In the case of early termination of the clinical investigation, the date of the early termination shall be deemed to be the date of the end of the clinical investigation.

16.3 REQUIREMENTS FOR PATIENT FOLLOW-UP AND CONTINUED CARE

In the case of temporary halt or early termination of the investigation, the requirements for patient follow-up will depend on the circumstance of the temporary halt or early termination:

- For reasons not affecting the benefit-risk balance, according to the Sponsor recommendations, the investigator could decide if the patient may continue the clinical investigation as planned or if the patient should be withdrawn from the investigation.
- For reasons of a change of the benefit-risk balance, the patient should be withdrawn from the investigation and the IMD must be discontinued.
- For an exceptional reason (e.g. COVID-19 pandemic), each investigator has to decide whether the patient continued the investigation when able to follow the CIP requirements safely or to withdraw the patient from the investigation, based on his/her assessment of the benefit/risk ratio regarding the Covid-19 pandemic situation in his/her country/region and own investigational site, in accordance with the national/regional recommendations.

This concerns all patient still on-going in the clinical investigation at the time of temporary halt or early termination.

If a patient is prematurely stopping the IMD or should prematurely withdraw from the investigation, the investigator must perform at least one premature discontinuation visit following by one/several follow-up visits as decided by the Sponsor and according to the circumstances.

If possible and depending the circumstance, the premature discontinuation visit will be realized on site and the follow-visit(s) could be performed by phone.

If it is not possible, the premature discontinuation visit will be performed by phone-call and/or online video consultation. In this case and if current circumstances are favorable, at least one of follow-up safety visit should be performed onsite.

During the premature discontinuation visit/phone-call, the investigator has to:

- Collect AE/SAE
- Check the IMD compliance
- Check the number of returned used and unused IMD
- Instruct the patient to stop or to continue the IMD (depending on the reason as described above)
- Ensure the continuity of investigational disease medication (if appropriate)
- Perform evaluations described for the premature investigation discontinuation/final visit if possible (onsite visit)
- Prescribe to the patient the best appropriate treatment if needed
- Collect information on concomitant medications changes.

If some follow-up visit(s) are required or if the premature discontinuation visit could not be realized on site, the investigator will have to schedule these phone-calls/visits. During this/these visit(s), the investigator has to:

- Collect AE/SAE
- Collect information on concomitant medications changes
- Check the IMD compliance, if applicable
- Check the number of returned used and unused IMD, if applicable
- Perform evaluations described for the premature investigation discontinuation/final visit if not done at the premature discontinuation visit
- Prescribe to the patient the best appropriate treatment if needed.

The role of investigator-masked and Unmasked collaborator will be the same as previous visits.

In any case, the requirements for patient follow-up will be described in more details in specific guidelines which will be provided to each involved person (investigators, Investigational team, Hospitals etc...) and to Institutions if necessary (IEC, CA etc...). This could be done by submitting a notification (in case of emergency) and/or a substantial modification.

17. PUBLICATION POLICY

By signing the CIP, the investigator agrees that the results of the investigation may be used for the purposes of national and international registration, publication, and information for medical and pharmaceutical professionals. If necessary, the CAs will be notified of the investigator's name, address, qualifications, and extent of involvement.

The data resulting from this investigation will be the proprietary information of Sponsor. An investigator shall not publish any data (poster, abstract, paper, *etc.*) without having consulted with Laboratoires THÉA in advance.

At the end of the investigation, Laboratoires THÉA will prepare a Clinical Investigation Report. The draft reports will be discussed with the coordinating investigator and with Laboratoires THÉA.

For any manuscript for publication prepared by Laboratoires THÉA, Laboratoires THÉA reserves the right to select the investigators who will be the authors to review the manuscript. Laboratoires THÉA will allow the selected investigators sufficient time for full review of the manuscript before publication.

1 INTRODUCTION

The purpose of this Statistical Analysis Plan (SAP) is to provide a description of the statistical methods to be implemented for the analysis of data from the clinical investigation with Clinical Investigation Plan (CIP) No. LT2769-002, version 2.0 dated 15.06.2023 (LT, 2023).

This SAP is based on the electronic Case Report Form (eCRF) version 4.0 dated 29.05.2024.

The analyses follow the guidelines from the International Organization for Standardization (ISO) described in ISO 14155 Clinical investigation of medical devices for human subjects -- Good clinical practice (ISO 14155).

[figure not shown]
The SAP will be finalized prior to database lock. Any deviations from the SAP after database lock will be documented in the final Clinical Investigation Report (CIR).

2 STUDY OVERVIEW

2.1 Study Objectives

2.1.1 *Primary Objective*

The primary objective of the investigation is to demonstrate the non-inferiority of T2769 versus Vismed® Multi in terms of total ocular surface staining (Oxford score) in patients with Dry Eye Syndrome (DES), after 35 days of treatment.

2.2 Study Design

2.2.1 *Overview*

This investigation consists in a 5-week, international, multicentre, randomised, investigator-masked, 2-parallel-group (T2769 versus Vismed® Multi) confirmatory clinical investigation, planning to randomise 250 patients.

The investigation period for a patient is split into two parts, with a total maximum duration of 49 days:

- 7 to 10 days of run-in period with preservative-free artificial tears (Hydrabak®, NaCl 0.9%)
- 36 to 39 days of treatment period with the Investigational Medical Device (IMD): either T2769 or Vismed® Multi.

Four visits are scheduled during the course of the investigation:

- Visit #1: Day 1-10/Day 1-7: Screening visit (run-in period)
- Visit #2: Day 1: Randomisation visit (D1)
- Visit #3: Day 15 (± 1 day): (D15)
- Visit #4: Day 36 (+3 days): Final or premature discontinuation visit.

The detailed Schedule of Visits and Procedures is described in Table 2 of the CIP [REDACTED]

2.2.2 *Randomisation and Masking*

Patients are randomised stratified by site on a 1:1 basis to T2769 or Vismed® Multi respectively. The randomisation code list and the lists of IMDs numbers for the packaging is generated by the Interactive Web Response System (IWRS) provider, the randomisation and the IMD kits numbers are allocated to the patients according to randomisation list using an Interactive Response Technology (IRT).

Randomisation occurs at Randomisation visit (Day 1; Visit #2) after all procedures have been performed and eligibility for the investigation confirmed.

This is an investigator-masked clinical investigation, a double-masked investigation design not being possible due to different commercial packaging between T2769 and Vismed® Multi.

The masked investigator remains masked to the IMD (T2769 or Vismed® Multi). The masked investigator does not receive the returned IMDs from the patients.

The following-up of returned IMDs is delegated to an unmasked collaborator throughout the clinical investigation. The unmasked collaborator is in charge of recording the used/unused IMDs.

Masking is achieved by coding the interventions, providing each product unit with identical cardboard box and by identifying it by an IMD kit number.

The code should not be broken except:

- in case of medical emergency (where knowledge of the IMD received would affect the treatment of the emergency),
- or when it is a regulatory requirement (e.g., for Unanticipated Serious Adverse Device Effect [USADE]).

The investigator is responsible for accessing the IRT system to obtain the name of the IMD received by the patient.

If an emergency code breaking becomes necessary, the investigator should notify the Sponsor.

When a code is broken, the date, time and reason must be recorded in the patient's source, and in any associated Adverse Event (AE) report. The identity of the IMD should not be disclosed in these documents.

Further to an USADE assessment by the Global Drug Safety & Medical Information Department, the code might be broken for reporting purposes. The relevant Laboratoires Théa, Contract Research Organization (CRO), masked investigator and masked staff remain unaware of the identification of the IMD as per the above-mentioned process.

The overall randomisation list will be broken for data analysis after database lock.

2.2.3 *Hydrabak® and Investigational Medical Device*

The dose regimen of Hydrabak® and of the IMD is 1 drop in each eye, from 3 to 6 times daily, and the route of administration is topical, ocular use.

2.2.4 *Sample Size Determination*

[figure not shown]
The sample size is driven by the statistical hypotheses on the primary [REDACTED] endpoint [REDACTED]

2.3 Study Endpoints

2.3.1 Primary Performance Endpoint

The primary performance endpoint is the change from baseline (D1) in total ocular surface staining assessed on Oxford 0-15 scale, in the study eye at the D36 visit.

[figure not shown]
Baseline is defined in section [3.1.3](#) [REDACTED]

2.3.3 Safety and Tolerability Endpoints

The safety endpoints are:

- Treatment Emergent Adverse Event (TEAE) by System Organ Class (SOC) and Preferred Term (PT) (separately for ocular and systemic TEAE)

[figure not shown]

3 STATISTICAL METHODOLOGY

3.1 General Considerations

3.1.1 Analysis Day

The day of randomisation will be Day 1, and the day immediately before Day 1 will be Day -1. There will be no Day 0.

3.1.3 Definition of Baseline

Baseline is defined as the assessment at randomisation visit (D1) before the first IMD instillation.

Missing value at randomisation visit (D1) will not be replaced.

The change from baseline at a given visit is defined as the difference between the assessment at the given visit and the baseline.

3.1.5 *Summary Statistics*

Categorical data will generally be summarized with number of non-missing observations (n), counts and percentages of patients in each modality. Associated two-sided 95% CI for proportions will be calculated using the scoring method of Wilson without continuity correction. The missing values will not be counted for the percentage calculation.

Continuous data will generally be summarized with mean (with associated two-sided 95% CI), median (with associated two-sided 95% CI), standard deviation (SD), lower quartile (Q1), upper quartile (Q3), minimum, and maximum.

Generally, the minimum and maximum values will be reported to the same number of decimal places as the original values. The mean, median, quartiles and CIs will be reported to one additional decimal place, and the SD will be reported to two additional decimal places.

For endpoints defined as change from baseline, descriptive statistics and the change from baseline will be presented by visit.

Parameters recorded for both eyes will be described separately for the study eye and for the contralateral eye.

3.1.7 *Handling of Missing Data*

3.1.7.1 *Missing Data Handling for Primary [REDACTED] Endpoint*

For the primary performance endpoint analysis performed on FAS, Mixed Model for Repeated Measures (MMRM) method will be applied. MMRM method assumes missing data are Missing at Random (MAR) and no explicit imputation of missing assessments for a given visit time point will be performed. [REDACTED]

[REDACTED]

3.2 Analysis Sets

3.2.1 *Enrolled Set*

All patients who have signed the informed consent form and for whom the inclusion visit has been recorded in the eCRF.

3.2.2 *Safety Set*

All enrolled patients, having received at least one dose of IMD and analysed as treated.

The safety set will be the primary population for safety analysis.

3.2.3 *Intent-To-Treat (ITT) Set*

All randomised patients and analysed as randomised.

[figure not shown]
3.2.4 *Full Analysis Set (FAS)*

All randomised patients, having received at least one dose of IMD, with at least one baseline and one post-randomisation performance assessment and analysed as randomised.

The FAS will be the primary population for performance analysis.

3.2.5 *Per Protocol (PP) Set*

Subset of the FAS including patients without any major CIP deviations likely to seriously affect the primary [REDACTED] outcome of the study

Deviations from the CIP will be defined and assessed as “minor” or “major” in cooperation with the Sponsor during a blind review meeting before the database lock. A list of patients with major deviations from the CIP leading to exclusion from the PP set will be finalized prior to unblinding the randomised treatment assignments.

The PP set will be considered as secondary population and will be used for sensitivity analyses of the primary [REDACTED] endpoint. Patients will be analysed as treated.

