6.1.6 Procedures for the Replacement of Patients

The number of randomised patients will be followed in order to obtain at least 226 evaluable patients in the FAS population.

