6.3.8 Number of Patients Required to be Randomised in the Clinical Investigation

It is planned to randomise 250 patients in order to have 226 evaluable patients (113 per group) for the FAS analysis.

Evaluable patients will be defined as randomised patients having received at least one dose of IMD and with at least one performance endpoint post-randomisation visit.

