7.1 ANALYSIS POPULATION AND PROCEDURES

The following analysis sets will be considered:

- **Safety set:**

All enrolled patients, having received at least one dose of IMD and analysed as treated.

The safety set will be the primary population for safety analysis.

- **Intent-to-treat (ITT) set:**

All randomised patients and analysed as randomised.

- **Full analysis set (FAS):**

All randomised patients, having received at least one dose of IMD, with at least one baseline and one post-randomisation performance assessment on treatment and analysed as randomised.

The FAS will be the primary population for performance analysis.

- **Per protocol (PP) set:**

[figure not shown]
Subset of the FAS including patients without any major CIP violations likely to seriously affect the primary outcome of the study. Deviations from the CIP will be defined and assessed as “minor” or “major” in cooperation with the Sponsor during a blind review meeting before the database lock.

The PP set will be considered as secondary population and will be used for sensitivity analyses of the primary [REDACTED] endpoints. Patients will be analysed as treated.

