7.15 PROCEDURES FOR REPORTING ANY DEVIATION(S) FROM THE ORIGINAL STATISTICAL PLAN

Any changes from the planned analyses will be described and justified in the SAP and the final clinical investigation report.

7.17 DEFINE A STRATEGY FOR POOLING DATA, IF APPLICABLE.

Not applicable.

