3.4.1 Primary Performance Endpoint

The primary objective is to demonstrate the non-inferiority of T2769 compared to Vismed® Multi in terms of total ocular surface staining (Oxford score) after 35 days of treatment. The primary

performance endpoint is the change from baseline (D1) in total ocular surface staining assessed on Oxford 0-15 scale, in the study eye at the D36 visit. [REDACTED]

[REDACTED]

[REDACTED]

Primary Analysis

The inferential analyses of the primary performance endpoint will aim to assess the non-inferiority of T2769 to Vismed® Multi.

The hypothesis of non-inferiority of T2769 compared to Vismed® Multi will be tested by calculating the bilateral 95% CI of the difference between groups (T2769 – Vismed® Multi) of the total ocular surface staining (Oxford score) at D36 in the study eye in the FAS.

The non-inferiority of T2769 to Vismed® Multi on the total ocular surface staining (Oxford score) will be primarily tested using an MMRM approach.

The model will include treatment and scheduled visit time points (D15 and D36) as fixed factors, patient as random factor, and baseline total ocular surface staining (Oxford score) as continuous covariate. Treatment by scheduled visit time point and baseline total ocular surface staining (Oxford score) by scheduled visit time point will be included as interaction terms in the model. [REDACTED]

[REDACTED]

[REDACTED]

[REDACTED]

[figure not shown]
[REDACTED]

LS means and corresponding standard errors for change from baseline at each analysis visit will be provided for each treatment group. The difference in LS means between T2769 and Vismed® Multi, corresponding standard error, and the two-sided 95% CI for treatment effect (difference T2769 - Vismed® Multi) will be estimated at each analysis visit in this model. Non-inferiority will be achieved if the upper bound of the two-sided 95% CI for the difference between treatment groups (T2769 - Vismed® Multi) at D36 is lower than the margin of 2 points.

Descriptive summary statistics on the values and changes from baseline will be presented for the total ocular surface staining (Oxford score) at each analysis visit by treatment group.

The mean and associated SD of the Oxford score in the study eye will be graphically displayed for each treatment by analysis visit in the FAS.

[REDACTED]

[figure not shown]

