6 CHANGES FROM CIP-SPECIFIED STATISTICAL ANALYSES

The following changes from the protocol-specified statistical analyses have been made:

- Addition of the Enrolled set

- Individual patient data listings, separately for ocular and systemic AEs, are not provided for SAEs and IMD-related SAEs.

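### Does dropping the on-treatment condition from the FAS definition, between protocol and SAP, put the primary analysis at risk?

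*SAP*

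**What the plan says.** Protocol 7.1 and SAP 3.2.4 both make the FAS the primary population for performance. Both require randomisation and at least one dose of the device. They then differ by two words:

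- Protocol 7.1: "with at least one baseline and one post-randomisation performance assessment on treatment and analysed as randomised".
- SAP 3.2.4: "with at least one baseline and one post-randomisation performance assessment and analysed as randomised".

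Protocol 6.3.8 plans 250 randomised patients in order to have 226 evaluable for the FAS analysis, 113 per group. It defines evaluable patients as "randomised patients having received at least one dose of IMD and with at least one performance endpoint post-randomisation visit". Protocol 6.1.6 says randomisation will be followed "in order to obtain at least 226 evaluable patients in the FAS population".

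On declaring changes, protocol 7.15 states: "Any changes from the planned analyses will be described and justified in the SAP and the final clinical investigation report". SAP 6 opens with "The following changes from the protocol-specified statistical analyses have been made". In the public copy it then shows two items: the added Enrolled set and a reduction in adverse event listings.

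The primary model (SAP 3.4.1) is an MMRM with D15 and D36 as the scheduled time points and baseline Oxford score as covariate. The treatment difference "will be estimated at each analysis visit in this model", and non-inferiority is judged at D36 against a margin of 2 points.

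**The concern.** In a confirmatory trial the primary population should be fixed in one wording before unblinding. Here a condition in the protocol is absent from the SAP, and the section kept for such changes does not visibly mention it, although it does record smaller matters. A reader could fairly ask whether the primary set was altered without a reason being given.

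The difference also touches real patients. Someone who stops before D15 is examined at a premature discontinuation visit held after the stop (protocol 6.1.4). If that is the only post-baseline assessment, the SAP includes the patient, while protocol 7.1, read literally, does not. SAP 2.2.1 gives that visit the same label as the final one: "Visit #4: Day 36 (+3 days): Final or premature discontinuation visit". If such a score were analysed as D36, it would enter the primary estimate. The count of 226, against which randomisation is tracked, might also depend on which text is followed.

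**Working it through.** **1. The three texts side by side**

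| Condition | Protocol 7.1 (FAS) | SAP 3.2.4 (FAS) | Protocol 6.3.8 (evaluable) |
|---|---|---|---|
| Randomised, at least one dose | yes | yes | yes |
| Baseline performance assessment | yes | yes | not stated |
| Post-randomisation performance assessment | yes | yes | yes |
| That assessment on treatment | yes | no | no |

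Protocol 6.3.8 defines a count for enrolment, not the analysis set, so there are two FAS definitions and one related definition.

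**2. The baseline condition excludes almost nobody.** It asks for any baseline performance assessment. OSDI and the discomfort VAS are performance measures (protocol 6.4.1.2), and both are entry criteria at the randomisation visit (6.3.1). Randomisation follows the Day 1 procedures (6.1.2.1). Every eligible randomised patient therefore meets the condition, and SAP 3.2.4 and protocol 6.3.8 select in practice the same patients. A patient lacking only the baseline Oxford score contributes nothing to the primary model under any wording: baseline is a covariate and a missing value is not replaced (SAP 3.1.3).

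**3. The on-treatment condition.** Membership differs only for patients whose sole post-baseline assessment came after stopping the device, mainly those who stop before D15. Later stoppers normally have a D15 assessment on treatment and are in the FAS under both texts.

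**4. Effect on the primary estimate**

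- *Score assigned to neither D15 nor D36.* The patient has no response in the model, and no missing value is imputed (SAP 3.1.7.1). The shift is 0.
- *Score taken as D36.* Suppose k such patients join one arm of 113, each d points from that arm's baseline-adjusted mean, and the other 113 all have D36 values. The arm mean moves by about k × d / (113 + k).
  - d = 5, k = 1: 5/114 = 0.044 points, or 0.044/2 = 2.2% of the margin.
  - d = 5, k = 3: 15/116 = 0.129 points, or 6.5% of the margin.
  - d = 15, k = 1: 15/114 = 0.132 points.
  - d = 15, k = 3: 45/116 = 0.388 points.

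The last two lines are an outer bound. On a 0–15 score, a patient can lie 15 points from the arm mean only if that mean is exactly 0 or 15. All k patients are also placed in one arm; the same shift in both arms would cancel. The sign is unknown. Both k and d are assumptions.

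**5. Effect on the count of 226.** The plan allows for 250 − 226 = 24 losses, and 24/250 = 9.6%. The 226 cannot be rebuilt, because the sample-size inputs are not in the public text. By step 2, counting under the SAP wording agrees with protocol 6.3.8. Only the literal protocol 7.1 reading could lower the count. As an illustration, assume 226 gives exactly 80% or 90% power and m patients are lost:

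power = Φ(√((226 − m)/226) × (1.96 + z) − 1.96), with z = 0.842 (80%) or 1.282 (90%).

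- m = 3 (1% of 250, rounded up): 79.5% or 89.6%.
- m = 13 (5% of 250, rounded up): 77.6% or 88.2%.

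**The case for a change.** The strongest case for a change rests on principle, not size. Protocol 7.15 promises that changes will be described and justified in the SAP, SAP 6 exists to hold them, and a choice about the primary population is best recorded while the data are blinded. SAP 3.3.3 plans reasons for exclusion from the PP set only, so a reader of the tables would not see why FAS membership differs from the protocol text. Two or three sentences would settle it.

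The wording difference does stand. The rest of the case is weaker, for four reasons.

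- **Non-declaration cannot be shown.** The public SAP is redacted throughout, and SAP 6 may hold further items. Protocol 7.15 also names the final report as a place to describe changes.
- **Visit assignment is a separate question.** It arises for every early discontinuer, including those in the FAS under both texts. The rule may also be in text not shown: SAP numbering passes from 3.1.1 to 3.1.3, 3.1.5 and 3.1.7, and SAP 3.4.1 uses the term analysis visit as already established, beside redacted lines.
- **Safeguards exist.** Exclusions from the analysis sets are to be discussed at a blind review meeting before database lock (protocol 10), and SAP 3.3.3 tabulates and lists membership of every set.
- **The remedy leaves the analysis as it is.** It would keep the SAP 3.2.4 wording, the model, the margin and the success rule, and add only a log entry and a counting note.

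**Conclusion.** No change to the plan follows. The two FAS sentences do differ, and one wording in both would have been tidier. The sentence that governs the analysis is the SAP's, and it is sound: it does not remove randomised patients for something that happened after randomisation, and it agrees with protocol 6.3.8 on treatment status. An analyst who follows it as written gets a valid, more inclusive primary set.

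The patients affected are those with only an off-treatment assessment after baseline. Their number is not in the documents and is probably small. The shift in the primary estimate is 0 if their scores belong to no scheduled time point. It is 0.04 to 0.13 points against a margin of 2 if one to three of them, each 5 points from the mean, were counted at D36 in a single arm. These figures assume 113 other patients per arm with D36 values. The direction cannot be determined. Whether the sponsor recorded the change cannot be judged from a redacted copy. What remains is a matter of document harmonisation, with no gain for the planned analysis.
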